
clinical laboratory results from a minimum of 5 subjects in the current cohort),
 
 2. Escalate to the next planned cohort or alternative dose levels (e.g., lower, intermediate, or higher) in multiple-dose cohorts (based on a review of available data, including at least 48 hours post 7th dose safety data from a minimum of 5 subjects in the current cohort), 3. Add additional dose cohort(s) in either the single- or multiple-dose studies, 4. Increase the duration of dosing in the multiple-dose cohorts from 7 days to ≤ 14 days, 
In addition, if 2 or more subjects in a single cohort experience the same type of serious or medically significant event, further dosing will be withheld until the SRG investigates the events. Based on this assessment, the SRG will determine if the study should be terminated or continued and whether modification of planned dose levels and/or implementation of additional safety monitoring is indicated.
	

Primary Objective:
 
To characterize the safety and tolerability profile of escalating dose levels of CVN766 suspension when administered as a single oral dose or daily oral doses for 7 days in healthy subjects and determine the recommended phase 2 dose (RP2D).
	

Secondary Objectives:
 
 • To characterize the single-dose PK profile of CVN766 in plasma and CSF • To characterize the multiple-dose PK profile of CVN766 in plasma and CSF • To assess the effect of food on the bioavailability of CVN766 	

Exploratory Objectives:
 
 • To explore possible drug metabolic enzyme and transporter polymorphisms that may contribute to variability in CVN766 PK, pharmacodynamics, or safety 	

Subject Population: Healthy male and female subjects 18 to 55 years old
	

Number of Subjects:
 
Each dose cohort: 8 subjects (6 active:2 placebo) Estimated total: 64 subjects (5 single-dose cohorts, 3 multiple-dose cohorts)
	
Number of Sites:
 
2 (Australia)

Dose Level(s):
 
Planned single-dose levels are placebo, 5 mg, 15 mg, 45 mg, 125 mg, and 250 mg CVN766. Planned multiple dose levels are placebo, 45 mg, 125 mg, and 250 mg CVN766.
	
Route of Administration:
 
Oral

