
Duration of Treatment:
 
Single or daily oral doses for up to 7 days (+7 days as necessary to reach steady-state and as required by Safety Review Group).
	
Period of Evaluation:
 
Screening Period: up to 28 days Treatment Period: 1-7 days (+7 days, as necessary). Food Effect washout period (for select cohort only): at least 14 days Follow-up Period: approximately 14 days Total Duration:
 
 • Single-dose cohorts: approximately 6 weeks • Food effect cohort: approximately 8 weeks • Multiple-dose cohorts: approximately 7 weeks

Main Criteria for Inclusion:
	

Healthy male and female subjects who are 18 to 55 years of age, inclusive and have a body mass index (BMI) between 18.0 and 32.0 kg/m² inclusive at Screening.

A complete list of inclusion criteria is provided in **Section 7.1**.

Main Criteria for Exclusion:

Subjects have a known hypersensitivity to any component of the formulation of CVN766. Subjects have evidence of CS neurologic, cardiovascular, pulmonary, hepatic, hematopoietic disease, renal, metabolic, gastrointestinal, urologic, immunologic, endocrine disease, serious allergy, allergic skin rash, psychiatric disorder, or other abnormality that may impact the ability of the subject to participate or potentially confound the study results. Any finding in the subject's medical history, physical examination, or safety laboratory tests gives reasonable suspicion of a condition that might interfere with the conduct or interpretation of the study.

A complete list of exclusion criteria is provided in **Section 7.2**.

In addition, subjects may not use any excluded medications (including oral contraceptives as listed in Table 3), supplements, or food products. Concomitant medications and dietary products to be excluded are listed in Table 3.

Main Criteria for Evaluation and Analyses:

- Safety:

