6.1.2 Part 2: Multiple-Dose Regimen

For the multiple-dose regimen, approximately 24 subjects will be enrolled in 1 of the 3 multiple-dose cohorts (designated as M1 through M3, respectively) in an ascending fashion. Dosing will be administered in the fasting state; this can be changed by the SRG if exposure is found to be higher in the fed state. The dose levels planned to be studied in the multiple-dose regimen (M1 through M3) are provided in **Table 5**. Each multiple-dose cohort will consist of 8 subjects randomized to CVN766 or placebo, whereby 6 subjects will receive a daily dose of CVN766, and 2 subjects will receive matching placebo for 7 days. However, the duration may be increased to ≤14 days at the discretion of the safety review group (SRG) if preliminary PK data suggest steady-state will not be achieved within 6 days of daily dosing. Unlike the single-dose regimen, sentinel dosing within cohorts is not required in the multiple-dose regimen.

Subjects for all multiple-dose cohorts will be admitted to the study unit 1 day prior to dosing and remain in the unit for the duration of the dosing period and for at least 48 hours after the last dose for safety and PK assessments before discharge. On treatment Days 1 and 7, subjects will undergo safety monitoring and PK sampling from blood plasma through 48 hours post-dose and, in Cohort M1 only, from urine through 24 hours post-dose. In Cohorts M1 and M2, on treatment Day 7 (or last day of dosing, if extended beyond Day 7), subjects will undergo additional PK sampling from CSF via lumbar puncture at 3 hours post-dose. If the SRG determines additional PK sampling from CSF via lumbar puncture is not necessary for Cohort M2, the lumbar puncture may be omitted. Likewise, if needed to resolve questions arising from prior Cohorts’ data, subjects in Cohort M3 also may, at SRG discretion, undergo PK sampling from CSF via lumbar puncture, the choice of day (e.g., Day 1 or Day 7) and sampling time to be decided by SRG. Subjects in MAD cohorts may be asked to return to the clinic for an additional plasma PK sample 3 days after the last dose (e.g., Day 10) depending on emerging PK data, i.e., $t_{1/2}$. The total confinement period will be 9 nights unless extended for additional dosing days or management of AEs. Follow-up assessments will occur approximately 7 and 14 days after the final dose. A summary of multiple-dose study visits is included in **Appendix A**.

Table 2 Multiple Dose Visit Schedule

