6.3 Premature Termination or Suspension of Study or Investigational Site

6.3.1 Criteria for Premature Termination or Suspension of the Study

The study will be completed as planned unless new information or other evaluation regarding the safety of the study medication indicates an adverse change in the risk profile for the compound, such that the SRG or Institutional Review Board (IRB) considers the risk is no longer acceptable for subjects participating in the study.

In addition, if any of the following occur, further dosing will be withheld until the SRG reviews the relevant data, including unblinded data (if deemed necessary by the SRG request), and will decide whether it is safe to suspend dosing or continue dosing at either the planned or alternative dose levels or decides to prematurely terminate the study:

1. Two or more subjects in any single cohort or across more than 1 cohort experience the same type of serious or medically significant event as defined by the Investigator
2. Two or more subjects in any single cohort or across more than 1 cohort experience alanine aminotransferase (ALT) and/or aspartate aminotransferase (AST) elevations $>5 \times$ upper limits of normal (ULN) in the absence of a concomitant bilirubin increase (see point 3 below)

3. One or more subjects in any single cohort or across more than 1 cohort experience ALT and/or AST elevations $>3 \times \text{ULN}$ in the presence of a total bilirubin increase $>2 \times \text{ULN}$ or an international normalized ratio (INR) >1.5 without findings of cholestasis or other alternate etiology to explain the elevations (i.e., “Hy’s Law cases”)
4. Two or more subjects in any single cohort or across more than 1 cohort experience ALT and/or AST elevations $>3 \times \text{ULN}$ with the appearance of fatigue, nausea, vomiting, right upper quadrant pain or tenderness, fever, rash, and/or eosinophilia ($>5\%$).

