16. Subject who regularly use nicotine-containing products (including but not limited to cigarettes, electronic cigarettes, pipes, cigars, chewing tobacco, nicotine patch, or nicotine gum). The casual users (≤ 10 cigarettes/week) may participate but must agree to refrain from the time of Screening for the duration of the study or a positive urine cotinine test at Inpatient Check-in (Day -1).
17. Subject has poor peripheral venous access (defined as more than three failed attempts to cannulate).
18. Subject has donated or lost 450 mL or more of their blood volume (including plasmapheresis) or had a transfusion of any blood product within 45 days prior to Day 1.
19. Subject has an abnormal (CS) ECG at Screening or Inpatient Check-in (Day -1). Entry of any subject with an abnormal (NCS) ECG must be approved and documented by signature by the Investigator or medically qualified sub-Investigator.

20. Subject has a supine blood pressure outside the ranges of 90 to 140 mm Hg for systolic and 40 to 90 mm Hg for diastolic, confirmed with repeat per PI discretion at the Screening Visit or Inpatient Check-in (Day -1).
21. Subject has a resting heart rate outside the range of 40 to 100 bpm, confirmed with repeat per PI discretion at the Screening Visit or Inpatient Check-in (Day -1).
22. Subject has a QT interval with Fridericia’s correction method (QTcF) >450 ms (males) or >470 ms (females) or PR outside the range of 120 to 220 ms, confirmed with one repeat testing at the Screening Visit or Inpatient Check-in (Day -1) Visit.
23. Subject has abnormal Screening or Inpatient Check-in (Day -1) laboratory values that suggest a CS underlying disease or subject with the following lab abnormalities: ALT and/or AST >1.5 the ULN, confirmed with one repeat testing.
24. Subject has a risk of suicide according to the Investigator’s clinical judgment or has made a suicide attempt in the previous 2 years.

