7.5 Criteria for Discontinuation or Withdrawal of a Subject

The primary reason for discontinuation or withdrawal of the subject from the study or study medication should be recorded in the eCRF using the following categories. For screen failure subjects, **Section 9.1.15**.

1. The subject has experienced a PTE or AE that requires early termination because continued participation imposes an unacceptable risk to the subject's health or the subject is unwilling to continue because of the PTE or AE.
2. Liver Function Test (LFT) Abnormalities

Study medication should be discontinued immediately with appropriate clinical follow-up (including repeat laboratory tests until a subject's laboratory profile has returned to normal/baseline status) if the following circumstances occur at any time during study medication treatment:

- ALT or AST $>8 \times$ ULN, or
 - ALT or AST $>5 \times$ ULN and persists for more than 2 weeks, or
 - ALT or AST $>3 \times$ ULN in conjunction with elevated total bilirubin $>2 \times$ ULN or INR >1.5 , or
 - ALT or AST $>3 \times$ ULN with the appearance of fatigue, nausea, vomiting, right upper quadrant pain or tenderness, fever, rash and/or eosinophilia ($>5\%$).
3. Significant protocol deviation. The discovery post-randomization that the subject failed to meet protocol entry criteria or did not adhere to protocol requirements and continued participation poses an unacceptable risk to the subject's health.
 4. Lost to follow-up. The subject did not return to the clinic, and attempts to contact the subject were unsuccessful. Attempts to reach the subject must be documented.
 5. Voluntary withdrawal. The subject (or subject's legally acceptable representative) wishes to withdraw from the study. The reason for withdrawal, if provided, should be recorded in the eCRF.

Note: All attempts should be made to determine the underlying reason for the withdrawal, and, where possible, the primary underlying reason should be recorded (i.e., withdrawal due to an AE).

6. The sponsor, IRB, IEC, or regulatory agency terminates the study.
7. Other.

Note: The specific reasons should be recorded in the “specify” field of the eCRF.

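### In Section 7.5, the liver stopping criterion of ALT or AST above 5 × ULN for more than 2 weeks cannot be met during multiple-dose treatment, which lasts at most 14 days

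*Protocol*

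**What the plan says.** Protocol Section 7.5, item 2, gives the liver criteria for an individual subject. The action is "Study medication should be discontinued immediately with appropriate clinical follow-up", and it applies "if the following circumstances occur at any time during study medication treatment". Four alternatives follow, joined by *or*:

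- ALT or AST above 8 × ULN
- ALT or AST above 5 × "ULN and persists for more than 2 weeks"
- ALT or AST above 3 × ULN with total bilirubin above 2 × ULN or INR above 1.5
- ALT or AST above 3 × ULN with listed symptoms, rash or eosinophilia

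Section 7.6 obliges the investigator to discontinue a subject who meets the Section 7.5 criteria.

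On duration, the Study Summary gives "Treatment Period: 1-7 days (+7 days, as necessary". Section 6.1.2 sets the planned course, for placebo as for active: "2 subjects will receive matching placebo for 7 days". Among the powers of the Safety Review Group (SRG) in the Study Summary is "Increase the duration of dosing in the multiple-dose cohorts from 7 days to ≤ 14 days".

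At study level, Section 6.3.1 item 2 withholds further dosing when "Two or more subjects in any single cohort or across more than 1 cohort experience alanine aminotransferase (ALT) and/or aspartate aminotransferase (AST) elevations" above 5 × ULN without a concomitant bilirubin increase. It has no persistence condition.

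**The concern.** A criterion that needs more than two weeks of persistence, and is to be met while medication is being given, sits in a protocol whose longest course is two weeks. If it cannot be met before the last dose, the list offers a protection that is absent where daily dosing takes place.

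The subject affected is one in a multiple-dose cohort whose ALT or AST rises above 5 but not above 8 × ULN, with normal bilirubin and INR and without symptoms or eosinophilia. None of the other three criteria covers that subject. This is a first-in-human study, and Section 6.1.2 does not require sentinel dosing in the multiple-dose part, so the written stopping rules should work as they read.

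Sections 7.5 and 6.3.1 also sit awkwardly together. A value above 5 × ULN of any duration counts towards a hold on the whole study, yet at the same level the rule for the individual subject depends on a duration that the course cannot contain.

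**Working it through.** This is calendar arithmetic; no power or error-rate figure is involved.

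**Inputs**
- Persistence required: more than 14 days (Section 7.5).
- Maximum dosing: 7 + 7 = 14 days, which reproduces the limit in the Study Summary.
- Entry limit: Section 7.2 excludes subjects with "ALT and/or AST >1.5 the ULN, confirmed with one repeat testing" at Screening or Day -1. An eligible subject should therefore not enter with a known value above 5 × ULN.
- Laboratory tests in the multiple-dose part: before dosing each day from Day 1, so the first post-dose result is on Day 2 (Appendix A, multiple-dose schedule, note f). The schedule marks Day 6 as the model for any added dosing days, so daily testing is taken to continue in an extension.

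**Time available for persistence** = day of last dose − day of first value above 5 × ULN. As a generous bound, the final 24-hour dosing interval is also counted, and onset at the Day 1 pre-dose sample is allowed.

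| Regimen | First high value | At last dose | With final 24 h | More than 14 days? |
|---|---|---|---|---|
| 7 days | Day 2 | 7 − 2 = 5 | 8 − 2 = 6 | No |
| 7 days | Day 1 pre-dose | 7 − 1 = 6 | 8 − 1 = 7 | No |
| 14 days | Day 2 | 14 − 2 = 12 | 15 − 2 = 13 | No |
| 14 days | Day 1 pre-dose | 14 − 1 = 13 | 15 − 1 = 14 | No |

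The most favourable case reaches exactly 14 days, which is still not more than 14.

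**Course length needed.** The first daily test at which more than 14 days have passed is onset day + 15: Day 16 for onset on Day 1, Day 17 for onset on Day 2. A course of 16 or 17 dosing days would be needed before the criterion could stop a dose; the protocol allows at most 14.

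**Single-dose part.** In S1, S2, S4 and S5 there is no later dose to stop. In S3 there is one, the fed dose. Section 6.1.1 places it at least 14 days after the first dose, so on Day 15 at the earliest: 15 − 2 = 13 days from a Day 2 elevation, just short. Appendix A counts the interval from Day 8, so the return is on Day 8 + 14 = Day 22 at the earliest: 22 − 2 = 20 days, which is enough. The criterion can act in S3 if the gap is long enough.

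**The case against.** A reader might infer from the arithmetic that the liver stopping rule as a whole fails in the multiple-dose part. It does not. The four criteria are alternatives, three have no persistence condition, and those three can operate from the first post-dose test. An unreachable alternative disables none of the others.

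A reader might also infer that the subject described would necessarily receive every remaining dose. The documents do not support that either:

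- Section 7.5 item 1 covers an adverse event that makes continued participation an unacceptable risk, and Section 9.1.12 requires clinically significant laboratory abnormalities to be recorded as adverse events.
- Section 9.1.12 also requires repeat tests after any ALT or AST above 3 × ULN. If the value stays above that level on two consecutive occasions, the investigator must contact the Medical Monitor, and stopping medication is one of the matters to consider. With daily tests, the second value could come one day after the first.
- Section 6.1.3 has all adverse events up to discharge evaluated for subject or study termination.

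Further, Section 6.3.1 item 2 counts subjects across cohorts, so after one earlier case anywhere in the study the next case triggers the hold. The criterion also has a possible use before the S3 fed dose, and a subject-level rule need not mirror a two-subject study rule.

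All of this stands, and it limits the point. What it does not supply is a mandatory laboratory criterion for the first such subject. The three routes above depend on someone deciding to stop, and the study-level hold waits for a second subject. Reading the treatment window to include follow-up does not help, because by then no dose is left to stop.

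**Conclusion.** The point holds for one of the four liver criteria and for the multiple-dose part only, planned as three cohorts of 8 (about 24 subjects). There, the persistence criterion cannot be met before the last dose under either permitted course length: the longest run from a Day 2 finding is 5 or 12 days, against a requirement of more than 14.

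In practice, a multiple-dose subject with an isolated, asymptomatic ALT or AST above 5 and up to 8 × ULN has no mandatory laboratory criterion that stops dosing. Discretionary stopping remains, and so does the two-subject hold. How often such a subject would arise cannot be derived from the documents and is not estimated here.

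The conclusion takes two weeks as 14 days, counts persistence from the first laboratory value above the threshold, and assumes that the SRG extends dosing to no more than 14 days. It is a matter of subject safety and internal consistency; no endpoint or analysis depends on it.

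**What to change.** The sponsor's medical team should reconcile the persistence condition in Section 7.5 with the 7-day (up to 14-day) multiple-dose treatment period, and with Section 6.3.1 item 2, which uses the same threshold without a duration. If the criterion is meant to act only before the S3 fed dose, and stopping in the multiple-dose cohorts is meant to rest on judgement for values above 5 and up to 8 × ULN, Section 7.5 should say so. Which threshold or timing is right is a clinical decision, and none is proposed here.

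The cost is one bullet in Section 7.5, with a check that Sections 6.3.1 and 9.1.12 still agree with it. Sample size, visit schedule and analysis are unaffected.

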7.6 Procedures for Discontinuation or Withdrawal of a Subject

The Investigator must discontinue a subject’s study participation at any time during the study when the subject meets the study discontinuation criteria described in **Section 7.5**. In addition, a subject may discontinue their participation without giving a reason at any time during the study. Should a subject’s involvement be terminated, the primary criterion for termination must be recorded by the Investigator. In addition, efforts should be made to perform all procedures scheduled for the Early Termination Visit. Discontinued or withdrawn subjects may be replaced at the Sponsor’s discretion.

Participants who withdraw from the study prior to dosing may be replaced. If a participant withdraws after the first dose of study medication or placebo, no replacement will occur.

8.0 CLINICAL TRIAL MANAGEMENT

8.1 Study Medication and Materials

This section contains information regarding all medication and materials provided directly by the sponsor and/or sourced by other means required by the study protocol, including important sections describing the management of clinical trial material.

8.1.1 Dosage Form, Manufacturing, Packaging, and Labeling

Study drug refers to CVN766 and matching placebo. Study drug will be provided in bulk supply. An unblinded pharmacist will manage and prepare doses as oral suspensions as needed throughout the study.

In this protocol, the term study medication refers to all or any of the drugs defined below.

8.1.1.1 Investigational Drug

CVN766 and Matching Placebo

CVN766 drug substance is stored at room temperature. CVN766 oral suspension and matching placebo should be stored according to instructions in the Pharmacy Manual.

8.1.3 Dose and Regimen

The Investigator or Investigator's designee will instruct the subject on dosing procedures.

All dosing will occur while subjects are in the clinic under the supervision of the Investigator and in fed or fasting conditions as outlined in **Section 7.4**.

The exact time of dose will be recorded in the source documents and on the appropriate eCRF.

The planned dose levels to be studied are provided in **Table 5**. If the planned highest dose level does not reach the desired exposure, then additional cohorts with higher dose levels may be considered. If all planned dose levels are not tolerated in an earlier cohort, the following cohorts may study lower doses at the discretion of the Investigator and the SRG. The actual choice of the subsequent dose level will occur after a full review of the available blinded safety, tolerability, and clinical laboratory results, and available PK data in the preceding cohort. The subsequent dose level may be higher, lower, or remain the same as the preceding dose level.

Table 5 describes the treatment and medication type that would be provided for each cohort.

Table 5 Planned Single and Multiple Dose Levels by Cohort

Single-Dose Cohorts			
Cohort	Planned Treatment*	No. of Subjects	Medication Type
S1	CVN766 5 mg	6	oral suspension
	Placebo	2	oral suspension
S2	CVN766 15 mg	6	oral suspension
	Placebo	2	oral suspension
S3 Fasted	CVN766 45 mg	6	oral suspension
	Placebo	2	oral suspension
S3 Fed (Same 8 subjects as in the S3 FASTED cohort)	CVN766 45 mg	6	oral suspension
	Placebo	2	oral suspension
S4	CVN766 125 mg	6	oral suspension
	Placebo	2	oral suspension
S5	CVN766 250 mg	6	oral suspension
	Placebo	2	oral suspension

Multiple Dose Cohorts

Cohort	Planned Treatment*	No. of Subjects	Medication Type
M1	CVN766 45 mg	6	oral suspension
	Placebo	2	oral suspension
M2	CVN766 125 mg	6	oral suspension
	Placebo	2	oral suspension
M3	CVN766 250 mg	6	oral suspension
	Placebo	2	oral suspension

* Dose (active or placebo) is in 10 mL of suspension.

